7.4. Vital Signs and Abnormalities

Descriptive statistics of pulse/heart rate, blood pressure (systolic and diastolic) (sitting/semi- recumbent), weight, and body temperature values will be summarized at baseline and post baseline visits, and changes from baseline will be summarized for post baseline visits based on the Safety Population. A separate listing will include all the vital sign measurements, including those from the unscheduled visits.

The following post-baseline vital signs will be summarized based on the Safety Population:

- Maximum post-baseline in SBP:
 - No increase
 - Increase < 20 mmHg
 - Increase $\geq 20 \text{ mmHg}$
 - \geq 160 mmHg and increase \geq 20 mmHg
- Maximum post-baseline in DBP:
 - No increase
 - Increase < 20 mmHg
 - Increase \geq 20 mmHg
 - ≥ 100 mmHg and increase ≥ 20 mmHg

For the number of subjects meeting each category for the post-baseline results or for the change from, the numerator is the number of subjects with meeting the criterion at any post-baseline including the unscheduled, and the denominator is the number of subjects with normal baseline and at least one post baseline assessment including unscheduled visits in the Safety Population.

A listing for patients with any post-baseline potentially clinically significant changes listed above will be also presented.

Box plots for percent changes from baseline over time will be produced by combining module 1a and 1b based on the Safety Population and the number of patients with data at the relevant timepoints.

7.5. 12-lead ECG

Descriptive statistics (n, mean, SD, median, minimum, and maximum) of ECG parameters, including PR interval, RR interval, QRS duration, QT interval, and QTcF interval (Fridericia's corrections) will be presented for baseline, eachpost-baseline visit, and change from baseline to each post baseline visit for Safety Population. All measurements, including those during unscheduled visits, will be provided in data listings, but only the scheduled measurements will be included in the by-visit summary. The average of triplicate 12-lead ECG results will be used for descriptive statistics.

Overall ECG interpretation category (normal, abnormal NCS (not clinically significant), abnormal CS (clinically significant), and not evaluable) is collected in the CRF at baseline and each scheduled post-baseline visit. Shifts in ECG interpretation at baseline to worst post baseline will be presented. For triplicate 12-lead ECG results collected at a visit, the average of triplicate 12-lead ECG results will be used as the interpretation at baseline as well as post-baseline.

The QTcF will be categorized into the following categories.

- QTc interval >450 msec and ≤480 msec
- QTc interval >480 msec and ≤500 msec
- QTc interval >500 msec

The change from baseline in QTcF will also be categorized separately as follows:

- QTc interval increases from baseline by >30 msec and ≤60 msec
- QTc interval increases from baseline by >60 msec

For the number of subjects meeting each category for the post-baseline results, the numerator is the number of subjects with meeting the criterion at any post-baseline including unscheduled visits and the denominator is the number of subjects with normal baseline and at least one post baseline assessment including unscheduled visits in the Safety Population. For the number of subjects meeting each category for the change at post-baseline from baseline, the numerator is the number of subjects with meeting the criterion at post-baseline and the denominator is the number of subjects with baseline and at least one post baseline assessment in the Safety Population.

Box plots for absolute and pchange from baseline for QTcF will be produced by combining module based on the Safety Population and the number of patients with data at the relevant timepoints. All ECG parameters will be listed in a data listing. All ECG tables and listings will be reported on the safety analysis set.

A separate analysis on correlation between exposure and QTc will be performed as part of the population PK/ER analysis (outside the scope of this SAP).

7.6. Physical Examination and ECOG Performance Status

Abnormalities identified from physical examination will be listed for the safety analysis set.

Shift table of baseline ECOG performance to worst post-baseline status will be summarized as the number and % of patients in each ECOG category based on the Safety Population.

Any change in PE findings assessed as clinically significant should be recorded as an AE or SAE.

8. EFFICACY DATA

The efficacy analysis will be summarized by dose combination. Data from the backfill cohorts will be pooled with patients from the Dose Finding Phase that were treated at the RP2D (a minimum of 6 patients are expected to be treated at the RP2D during dose finding) when applicable.

Efficacy data will be summarized using the Efficacy Population.

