If anti-tumor activity is observed at a dose level that is lower than the current dose level being explored (after escalation has proceeded to a higher dose level), additional patients (N≤6), preferably with the same tumor/genomic alteration, may be enrolled at the lower dose level to further confirm safety and efficacy at that dose level. The relevant DLTs from the backfill cohorts will be included in the MTD and RP2D determination by the SRC. Additionally, intrapatient dose escalations for patients at a lower dose level will be allowed at the discretion of the Investigator, and with Sponsor approval and guidance by the SRC, if the higher dose level was deemed safe by the SRC.

Figure B: Module 1a and 1b Escalation Schema Module 1a: RP-6306 + FOLFIRI **MTD** Module 1b: RP-6306 + FOLFIRI Dose Finding (14 Day Cycles) Dose Finding (14 Day Cycles) RP-6306 Continuous QD FOLFIRI Days 1 and 2 RP-6306 3 Days On / 4 Days Off FOLFIRI Days 1 and 2 **MTD** Level R: DLT Safety or intolerability Cohort sizes at each dose level will be guided by BOIN drug combination criteria Cohort sizes at each dose level will be guided by BOIN drug combination criteria

BOIN=Bayesian optimal interval; DLT=dose-limiting toxicity; MTD=maximum tolerated dose;

Table A: **Dose Escalation Tables**

(A1) Dosing Regimens for Module 1a (Continuous RP-6306)^a

Treatment Frequency	Drug	Route of Administration	Dose Level 1 ^b (Starting Dose)	Dose Level 1 ^b and above	Dose Level R	Dose Level R+1°	Dose Level R+N ^c
Once Daily	RP-6306	Oral	40 mg	120 mg, then escalation up to 100%	Same as Current Dose Level	Per BOIN rules up to 20%-50% increase or MTD in MYTHIC	Per BOIN rules up to 20%-50% increase or MTD in MYTHIC
	Irinotecan	IV over 30-90 min	180 mg/m^2	180 mg/m^2	Same as Current Dose Level	Up to 180 mg/m ²	Up to 180 mg/m²
FOLFIRI	Leucovorin	IV over 30-90 min concurrently with irinotecan	400 mg/m ²	400 mg/m ²	Same as Current Dose Level	400 mg/m ²	400 mg/m^2
once every 2 weeks on	Fluorouracil	IV bolus after leucovorin	400 mg/m^2	400 mg/m^2	Same as Current Dose Level	400 mg/m ²	400 mg/m^2
Day 1 ^d				THEN			
	Fluorouracil	IV continuous infusion; start on Day 1 over 46 hours only	2400 mg/m ²	2400 mg/m ²	Same as Current Dose Level	2400 mg/m ²	2400 mg/m ²
1	* If Dose Level 1 is not tolerated						

	II Dose Level I is not tolerated					
Treatment Frequency	Route of Administration	Drug	Dose Level 1D ^c	Dose Level 2D ^c	Dose Level 3D ^c	
Once Daily	Oral	RP-6306	40 mg	40 mg	40 mg	

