The maximum total sample size for this study is 104 patients. The maximum sample size for the Dose Finding Phase is 36 evaluable patients per Module (72 patients total if an intermittent dosing schedule is initiated). The population used for determination of DLTs will consist of patients who have met the minimum safety evaluation requirements of the study, and/or who have experienced a DLT at any time during the initial 28 days (2 cycles) of the study. Minimum safety requirements will be met if, during the first 2 cycles of treatment, the patient receives at least 75% of planned total doses of RP-6306 for the evaluated schedule, 100% of planned doses of FOLFIRI, completes all required safety evaluations per Schedule of Assessments, and are observed at least until Day 28 since the first dose of study treatment. Thus, the possible total number per Module may be slightly higher at 40 patients (approximately +10%, 80 total patients). Depending on the toxicity profile of the combination and the number of dose levels required to establish the MTD/RP2D, the actual study sample size may vary. Approximately an additional 24 patients will be planned for backfill cohorts.

Analysis Populations

The following analysis populations will be used:

[figure not shown]
- DLT Evaluable Population for dose decisions will be as defined above.
- The Safety Population, used for the assessment of overall safety and tolerability, will consist of all patients who receive at least one dose of study treatment. Patients will be assessed for safety based on the dose level in which they were enrolled.
- The Efficacy Population, used for the assessment of efficacy, will consist of all patients who have measurable disease, are exposed to at least one dose of study treatment, and have local confirmation of their genomic alterations.
- The PK Population, used for the assessment of PK endpoints, will consist of all
 patients who have sufficient RP-6306, irinotecan, or SN-38 plasma concentration data
 recorded to derive PK endpoints.

Efficacy Analysis:

Approximately 24 additional patients will be enrolled in backfill cohorts ($N \le 8$ per cohort) to further evaluate the safety/tolerability profile in specific patient populations (eg, specific cancer types or patients that are high-risk for toxicities),

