The efficacy analysis will be summarized by dose combination and data from the backfill cohorts will be pooled with patients from the Dose Finding Phase that were treated at the RP2D (a minimum of 6 patients are expected to be treated at the RP2D during dose finding) when applicable.

Each cohort will be evaluated for ORR, best overall response rate, CBR, DOR, changes in tumor size, PFS at 6 months, and any available OS at 12 months.

Safety Analysis:

Toxicity will be summarized by grade and type. All AEs will be listed, including the verbatim description, system organ class, and preferred term.

Incidence of TEAEs, treatment-related TEAEs, TEAEs leading to death, SAEs, treatment-related SAEs, TEAEs leading to study treatment discontinuation or interruption, and TEAEs leading to dose modifications will be recorded. Clinically relevant laboratory abnormalities (ie, laboratory abnormalities that result in treatment modification or require intervention) will be recorded as AEs. TEAEs will be further summarized by severity (according to NCI CTCAE version 5.0). Changes in clinical laboratory parameters (eg, hematology, chemistry, urinalysis, etc.), CTCAE graded laboratory toxicities, vital signs, ECOG performance status, PEs, and usage of concomitant medications and procedures will be summarized.

PK Analysis:

PK parameters for RP-6306, irinotecan, and SN-38 will be calculated using noncompartmental analysis or other modeling methods as well as using a population PK model: AUC_{0-last} , C_{max} , and T_{max} , and other parameters as appropriate.

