3. INVESTIGATIONAL PLAN

3.1. Overall Study Design and Plan

This is a multicenter, open-label, Phase 1 study to evaluate the safety and preliminary efficacy of RP-6306, a first-in-class, membrane-associated tyrosine- and threonine-specific Cdc2-inhibitory kinase (PKMYT1) inhibitor, given on a continuous or, if necessary, intermittent schedule in combination with FOLFIRI for the treatment of patients with locally advanced or metastatic solid tumors (Figure 1). Eligible patients must have a CRC, GI, esophageal tumor, or other solid tumors harboring CCNE1 amplification, deleterious mutation in FBXW7 and/or other genetic alterations with mechanistic rationale agreed upon by the Sponsor and the Investigator and, in the opinion of the Investigator, are candidates for FOLFIRI treatment.

The study will follow a Bayesian Optimal Interval (BOIN) drug combination design to identify the MTD (dose level and dosing schedule for Module 1a and, if necessary, Module 1b) of RP-6306 and FOLFIRI. Backfill cohorts with specific molecular alterations or cancer types will be enrolled to further evaluate the PK, pharmacodynamic and mechanism of action biomarkers, safety and tolerability, and preliminary efficacy of the combination, as agreed upon by the Investigators and Safety Review Committee (SRC). The totality of safety, PK, pharmacodynamic, and preliminary efficacy data from each module will be used to establish a preferred RP2D and schedule.

Figure 1: Module 1 Study Schema

[figure not shown]
CCNE1=Cyclin E1; CRC=colorectal; FBXW7=F-box and WD repeat domain containing 7; GI=gastrointestinal; QD=once daily; RP2D=recommended Phase 2 dose.

Note: Additional schedules may be tested based on safety, tolerability, and drug exposure data generated in Modules 1a and 1b.

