- Dose escalation of RP-6306 will follow the BOIN criteria as guided by the SRC. RP 6306 can continue with increases of 20% to 50% (R+1).

Module 1b

[figure not shown]
If tolerability of continuous RP-6306 with FOLFIRI is limiting, Module 1b will be initiated if agreed upon by the SRC. In Module 1b, an intermittent dosing schedule of RP-6306 given 3 consecutive days on / 4 consecutive days off will be tested in combination with FOLFIRI. When Module 1b is initiated, the starting dose of RP-6306 and FOLFIRI will be the same as the highest total daily dose evaluated in Module 1a and will be given to a cohort of N≥2 patients. To allow better dose and schedule exploration early in the development, additional schedules may be evaluated that involve intermittent dosing (eg, 2 consecutive days on / 5 consecutive days off or 1 week on / 1 week off) depending on observed toxicities. The dose of RP-6306 or FOLFIRI will be increased or decreased per BOIN criteria independently of Module 1a until an MTD is established. Dose escalation decisions will be discussed with the SRC after at least 2 evaluable patients completing the first 2 14-day treatment cycles and based on the emerging safety and tolerability profile, and clinical PK/pharmacodynamic data across the entire patient population in Modules 1a and 1b.

In the event Modules 1a and 1b are explored concurrently, the Medical Monitor and SRC will prioritize slot allocation for each module. The highest dose level of RP-6306 in this study will not exceed the MTD

of RP-6306 monotherapy identified in the MYTHIC study for a given schedule. The totality of safety, PK, pharmacodynamic, and preliminary efficacy data will be used to select a preferred RP2D and schedule for RP-6306 and FOLFIRI.

If anti-tumor activity is observed at a dose level that is lower than the current dose level being explored (after escalation has proceeded to a higher dose level), additional patients (N≤6), preferably with the same tumor/genomic alteration, may be enrolled at the lower dose level to further confirm safety and efficacy at that dose level. The relevant DLTs from the backfill cohorts will be included in the MTD and RP2D determination by the SRC. Additionally, intrapatient dose escalations for patients at a lower dose level will be allowed at the discretion of the Investigator, and with Sponsor approval and guidance by the SRC, if the higher dose level was deemed safe by the SRC.

Figure 3: Module 1a and 1b Escalation Schema

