3.3. Sample Size Considerations

The maximum total sample size for this study is 104 patients. The maximum sample size for the Dose Finding Phase is 36 evaluable patients per module (72 patients total if an intermittent dosing schedule is initiated). The population used for determination of DLTs will consist of patients who have met the minimum safety evaluation requirements of the study and/or who have experienced a DLT at any time during the initial 28 days (2 cycles) of the study (Section 11.1 of the protocol). Minimum safety requirements will be met if, during the first 2 cycles of treatment the patient receives at least 75% of planned total doses of RP-6306 for the evaluated schedule, 100% of planned doses of FOLFIRI, completes all required safety evaluations per Schedule of Assessments (Section 12.1 of the protocol), and are observed at least until Day 28 since the first dose of study treatment. Thus, the possible total number per module may be slightly higher at 40 patients (approximately +10%; 80 total patients). Depending on the toxicity profile of the combination and the number of dose levels required to establish the MTD/RP2D, the actual study sample size may vary. Approximately, an additional 24 patients will be planned for backfill cohorts.

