8.2. Efficacy Analysis Methods

For overall response rate, ORR, and CBR, the number and percentage of patients along with an exact binomial 95% confidence interval (CI), using the Clopper-Pearson method, will be presented.

In general, summary of all efficacy endpoints will be provided by dose level separately for Module 1a and 1b patients.

The assessment of tumor efficacy will be based on the measurements recorded by the investigator.

A summary of the best objective response will be presented which will include the number and percentage of patients with a best response of CR, PR, SD, PD and NE.

Time-to-event endpoints (PFS) will be analyzed using the KM method and results will be summarized by the 25th, 50th and 75th percentiles, if estimable, with associated 2-sided 95% CIs. KM plots will be provided. For PFS, the number (%) of patients with an event and the number (%) of patients censored will also be presented. The rate of PFS at 16 weeks and 24 weeks will be derived from the corresponding Kaplan-Meier curves. The KM analyses for DOR may be replaced by descriptive summary of median, and quartiles with individual listing for responders if total confirmed responders are few and less than 5 patients.

Maximum reduction in tumor size will be summarized by n, mean, standard deviation, median, 25th quartile and 75th quartile, minimum and maximum. The spider plots displaying change in tumor size over time for each patient will also be provided for each module and dose/schedule group as described above.

In addition, waterfall plots showing the best percentage change from baseline (largest decrease or smallest increase in the absence of a decrease) in the sum of the TL sizes will be produced for each module by dose/schedule group indicating each patient' best objective response.

Swimmer plots will be produced for each module and dose/schedule group to show the duration of study treatment per patient with indicators for timing of response, progression or death, where applicable.

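### Where backfill is opened because activity was seen at a dose, pooling it with the patients who prompted it inflates that dose's expected ORR; show the two groups separately beside the pooled figure

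*SAP*

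**What the plan says.** The activity route into backfill is described in the protocol Synopsis, under dose finding: "If anti-tumor activity is observed at a dose level that is lower than the current dose level being explored", and escalation has moved on, that lower dose may be expanded. SAP 3.2.1 repeats the rule and gives its size: "additional patients (N≤6), preferably with the same tumor/genomic alteration, may be enrolled at the lower dose level". The stated aim is to confirm safety and efficacy there. Activity is not defined, and the expansion is optional.

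There are other routes. SAP 3.1 says: "Backfill cohorts with specific molecular alterations or cancer types will be enrolled to further evaluate the PK, pharmacodynamic and mechanism of action biomarkers", along with safety and preliminary efficacy. The protocol Synopsis, under Efficacy Analysis, describes backfill of up to 8 patients per cohort "to further evaluate the safety/tolerability profile in specific patient populations". On the total, SAP 3.3 says: "Approximately, an additional 24 patients will be planned for backfill cohorts".

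For analysis, SAP 8 says: "Data from the backfill cohorts will be pooled with patients from the Dose Finding Phase that were treated at the RP2D", where this applies, and expects at least 6 dose-finding patients at the RP2D. The protocol Synopsis has the same rule: "data from the backfill cohorts will be pooled with patients from the Dose Finding Phase that were treated at the RP2D". SAP 8.2 reports ORR, overall response rate and clinical benefit rate (CBR) with an "exact binomial 95% confidence interval (CI), using the Clopper-Pearson method". The protocol also says that each cohort is evaluated for ORR, but it does not say that a backfill cohort is evaluated apart from the dose-finding patients at the same dose, and SAP 8 and 8.2 do not repeat the sentence.

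**The concern.** An expansion opened to confirm an early signal is meant to supply fresh evidence. If its patients are pooled with those who produced the signal, the signal counts towards its own confirmation. Given that the expansion took place, the early patients' response rate is on average above the true rate, and adding unselected patients dilutes the excess without removing it.

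The trial has no comparator, so a reader of the pooled ORR at such a dose cannot tell this excess from drug effect. The route can reach the RP2D, because both documents allow an RP2D below the MTD. Nothing in the SAP would let a reader see afterwards which doses were affected, since neither the reason for opening a cohort nor a split of the results is required.

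**Working it through.** **The plan's own figures.** The documents give no ORR target, precision or power, so there is no ORR figure to reproduce. The stated maximum of 104 does reproduce: 36 evaluable per module plus about 10% is 39.6, taken as 40; 2 × 40 + 24 = 104.

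**Inputs from the documents.**
- Dose-finding patients at the dose before backfill, n: at least 6 expected at the RP2D (SAP 8); cohorts can start with 2 (SAP 3.2.1).
- Backfill patients, m: up to 6 (SAP 3.2.1) or up to 8 (protocol Synopsis, Efficacy Analysis). The two caps differ, so both are used.

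**Assumptions.**
- The trigger is at least one responder among the n patients.
- The true ORR p is varied, because no value is given.
- Backfill patients have the same true ORR as dose-finding patients.

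**Formula.** Let X be the number of responders among the n. The chance that backfill opens is P = 1 − (1 − p)^n. Given opening, the mean of X is np/P, and the backfill patients contribute mp. So

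expected pooled ORR = (np/P + mp)/(n + m).

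**Main case, n = 6 and m = 6.**

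| True ORR | P | (np/P + mp)/12 | Expected pooled ORR | Bias (points) |
|---|---|---|---|---|
| 10% | 0.469 | (1.280 + 0.6)/12 | 15.7% | +5.7 |
| 15% | 0.623 | (1.445 + 0.9)/12 | 19.5% | +4.5 |
| 20% | 0.738 | (1.626 + 1.2)/12 | 23.6% | +3.6 |
| 30% | 0.882 | (2.040 + 1.8)/12 | 32.0% | +2.0 |

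**Other sizes, bias in points.**

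| n + m | True 10% | True 20% | True 30% |
|---|---|---|---|
| 2 + 6 | +10.7 | +8.9 | +7.2 |
| 3 + 6 | +9.0 | +7.0 | +5.2 |
| 6 + 8 | +4.9 | +3.0 | +1.7 |
| 9 + 6 | +3.8 | +1.9 | +0.8 |

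**If backfill can also open without a response.** Suppose a 6 + 6 dose with no responder is still backfilled, for other reasons, half the time. The bias falls to +1.8, +1.5 and +0.9 points at 10%, 20% and 30%. If the dose would be backfilled whatever was seen, the bias is zero.

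**All doses together.** If doses that were not backfilled are counted at 0 out of 6, the average bias over all doses is downward: −2.7, −2.6 and −1.8 points at 10%, 20% and 30%. The upward bias belongs to the doses that were expanded.

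**Intervals.** Coverage of the Clopper-Pearson 95% interval, given that backfill opened, was between 92.8% and 99.5% in all cases run.

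**Accuracy of the two estimates.** Root-mean-square error in points, given opening, for 6 + 6:

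| True ORR | Pooled | Backfill only |
|---|---|---|
| 5% | 8.8 | 8.9 |
| 10% | 9.4 | 12.2 |
| 15% | 10.2 | 14.6 |
| 20% | 11.0 | 16.3 |
| 30% | 12.5 | 18.7 |

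The order reverses when few patients come first and the true ORR is low: for 2 + 6 at a true ORR of 10%, it is 14.3 pooled against 12.2 for backfill only.

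**The case against.** Several arguments limit the point.

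- **The trigger.** It is undefined activity, not a response, and expansion is optional. This stands: the sizes above depend on the assumed trigger.
- **Scope.** A reader might infer that all pooled backfill, or the pooled RP2D result in general, is biased. The documents do not support that. Backfill for tumor type, molecular alteration, PK, biomarkers or safety is not tied to a response. Nor can an RP2D that is the highest dose explored have been backfilled by the activity route.
- **Inclusion of the early patients.** A reader might also infer that they enter the estimate only because one of them responded. SAP 8 and 8.2 report efficacy by dose whatever the response. What depends on response is whether further patients are added.
- **Size.** With the 6 patients expected at the RP2D and a true ORR of 20% or more, the bias is about 1 to 4 points. If 3 patients prompt the backfill and 3 more dose-finding patients follow, the later 3 are not conditioned on response: at a true ORR of 15%, the expected value is (0.45/0.3859 + 9 × 0.15)/12 = 21.0%, against 23.0% for 3 + 6.
- **Remedy.** Making backfill-only the lead estimate would usually increase the total error, as shown above. It might also describe a narrower population, since these patients are preferably chosen with the same tumor or alteration. This stands, and it rules out replacing the pooled figure.
- **Existing safeguards.** The protocol's sentence on evaluating each cohort may have been meant to give the split, and SAP 8.2 adds patient-level plots. But the sentence leaves the cohort undefined, and the plots are by dose and schedule group, with no stated marking of backfill patients.

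**Conclusion.** The concern holds for doses backfilled because activity was seen there, and only for those. On the assumption of at least one response as the trigger and 6 + 6 patients, the expected pooled ORR exceeds the truth by 5.7 points at a true ORR of 10%, falling to 2.0 points at 30%. It is larger when 2 or 3 patients precede the backfill, and smaller where backfill may also open for other reasons.

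The harm is to the point estimate. Interval coverage is not materially affected. ORR is a secondary, descriptive endpoint with no success threshold, so no error rate is at stake. Choosing the RP2D partly on preliminary efficacy is a separate selection, which the change below does not remove. This is a worthwhile reporting improvement, not a flaw that undermines the trial.

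**What to change.** In SAP 8 and 8.2:

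1. Require that the reason each backfill cohort was opened be recorded when it is opened, including what was counted as activity.
2. For any dose backfilled because of observed activity, show ORR, best overall response rate, CBR and best percentage change in tumor size separately for dose-finding and backfill patients, beside the pooled figure.
3. Label that pooled figure as including the patients whose activity triggered the backfill.

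The pooled figure may stay as the lead estimate. The split adds one that is free of this trigger's bias. The per-cohort caps of 6 and 8 should be reconciled at the same time.

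The cost is SAP wording, a short record per cohort and one extra column per table. Enrolment, dosing and clinical data collection do not change. The drawback is precision: the backfill column rests on 6 to 8 patients, and 0 responders out of 6, for example, has an exact 95% interval of 0% to 46%.
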